### 5.6.2. Brain volume and functional connectivity

If data is available then changes in regional brain volume and functional connectivity in brain networks captured by MRI over the course of the study will be explored and summarised. MRI will be obtained every 8-12 weeks; therefore, an MMRM may be conducted fitting treatment and study visit and the interaction as fixed effects, the baseline will also be included and the baseline\*visit interaction will be assessed for potential inclusion. The following SAS code may be utilized for each relevant endpoint:

```
proc mixed data=MRI_sim;
  class patient treatment visit;
  model change_from_baseline_volume = treatment treatment*visit baseline_volume visit
  baseline*visit / outp=resdat s cl solution residual;
  random intercept/subject= patient type=un;
  lsmeans treatment*visit treatment /pdiff cl alpha=0.05;
  ods output lsmeans=lsmean1 diffss=diff1 covparms=cov1;
run;
```

Additionally, the relationship between LY3303560 serum exposure and imaging endpoints may be explored graphically or by a modeling approach.

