The dose range chosen for Study LMDD is based upon preclinical data and preliminary safety, tolerability and PK data from the ongoing single-dose study (LMDA). The highest planned dose is 210 mg, which is lower than the administered doses in Study LMDA that have been shown to be well tolerated. Preliminary data from Study LMDA indicate that LY3303560 is well tolerated up to 2800 mg when administered as a single IV dose, with no dose-limiting safety or tolerability findings to date. In Study LMDD, multiple IV doses of 70 mg have been administered to 9 patients with AD (7 LY, 2 placebo), and to date, no SAEs or infusion-related reactions have been reported.

In this current study, safety data for a particular dose cohort will be reviewed prior to dose escalation to the subsequent cohort (see Section 5.1.3). Safety data will be reviewed periodically during the treatment and follow-up periods.

More information about the known and expected benefits, risks, SAEs and reasonably anticipated AEs of LY3303560 are to be found in the Investigator's Brochure (IB).

4. Objectives and Endpoints

Table LMDD.1 shows the objectives and endpoints of the study.

Table LMDD.1. Objectives and Endpoints

| Objectives | Endpoints |
|---|---|
| 
Primary
 
The primary objective of this study is to assess the safety and tolerability after 16 weeks of multiple doses of LY3303560 in patients with MCI due to AD or mild to moderate AD
 | Safety and tolerability will be assessed by monitoring treatment-emergent adverse events (TEAEs) |
| 
Secondary
 
 • To assess the PK of LY3303560 in serum following multiple IV doses of LY3303560 in patients with MCI due to AD or mild to moderate AD | Maximum serum concentration (C_{max}) and the area under the serum concentration time curve during the dosing interval (AUC_{τ}) |

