10.1. Sample Size Determination

A total of 24 patients may be enrolled to ensure 16 complete the study. The sample size is customary for Phase 1 studies evaluating safety, PK and/or PD parameters.

It is expected that at least 4 Japanese patients will be enrolled into the study. Patients will be stratified by Japanese/non-Japanese but not by disease severity at randomisation.

Patients who are randomised but do not complete the study may be replaced to ensure that enough patients complete the study (see Section 5.2).

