- The Schedule of Activities (Section 2) has been amended to show that, after a patient has had 6 infusions with no infusion reaction, the observation period for subsequent infusions has been reduced to 2 hours. However, should any infusion reaction occur for any patient, the monitoring period will be increased to at least 8 hours for all subsequent infusions. To date, there have been no infusion reactions observed in 9 subjects in Cohort 1 (70 mg LY3303560) who have reached at least 6 months of dosing and 9 subjects in Cohort 2 (210 mg LY3303560) who have reached at least 3 months of dosing.

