## 5. A Priori Statistical Methods

### 5.1. General Considerations

Pharmacokinetic analyses will be conducted on the full analysis set (not including placebo). This set includes all data from all subjects receiving at least one dose of the investigational product.

Safety analyses will be conducted for all enrolled subjects who took study medication, whether or not they completed all protocol requirements.

Additional exploratory analyses of the data will be conducted as deemed appropriate. As this is a Phase 1 study and there will be no formal statistical hypothesis testing, any changes to the planned analysis will not necessitate a protocol amendment and will be detailed in the study report. Summary statistics, data tabulations, and data graphs by ethnicity (Japanese and non-Japanese, and combined) will be provided as appropriate.

Safety reporting will be conducted by Covance; with the exception of QTcF statistical analyses which will be conducted by Eli Lilly. All drug effects, PK, PD, imaging, cognition and exploratory reporting and analyses will be conducted by Eli Lilly.

Where two cohorts are given the same dose and formulation the patients will be pooled together and reported under the same dose levels. Placebo will be pooled across all cohorts.

In recognition that there are now only two dose cohorts in this study, any statistical models detailed in the analysis plan may still be carried out in order to estimate parameters, in particular where changes from baseline are being considered. Without recourse to statistical models, only those patients with both baseline and at least one post-baseline measurement can be included in any summary. Estimates from statistical models may provide additional information, if interpreted appropriately.

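### SAP 5.6.2: the MRI model code sets no degrees-of-freedom method, so limits for the visit-averaged treatment difference come out about 4.5% to 7% too narrow with 18 patients

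*SAP*

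**What the plan says.** SAP 5.6.2 offers optional code for a repeated-measures model of change in regional brain volume and functional connectivity, to be used for each relevant endpoint. The only covariance statement is "random intercept/subject= patient type=un", with no REPEATED statement. The MODEL statement ends "baseline*visit / outp=resdat s cl solution residual". In that list `residual` asks for residual diagnostics; it does not choose a degrees-of-freedom method. On the fixed effects, the text says that the "baseline\*visit interaction will be assessed for potential inclusion", while the code already includes that term. The results are requested with "lsmeans treatment*visit treatment /pdiff cl alpha=0.05", that is, differences at each visit and differences averaged over visits.

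There are three treatment groups (70 mg, 210 mg and placebo), because SAP 5.1 states "Placebo will be pooled across all cohorts". SAP 5.1 plans no formal hypothesis tests and keeps the models for estimation. Neither document names a degrees-of-freedom method.

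**The concern.** Each patient receives one treatment throughout. Further scans on the same patient sharpen that patient's mean but add no patients, so information on the visit-averaged treatment effect is limited by the number of patients. A df that rises with every scan credits the contrast with replication it does not have, and its confidence limits and p-values look more precise than they are. This is separate from whether a random intercept is the right covariance: it happens even when it is. Since the stated purpose of the models is estimation, the interval is their main product, and the same code would be reused across regions and networks.

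**Working it through.** **Inputs**

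- Patients: 18. SAP section 2 reports "9 subjects in Cohort 1 (70 mg LY3303560) who have reached at least 6 months of dosing and 9 subjects in Cohort 2". Protocol 3.3 describes Cohort 1 as "9 patients with AD (7 LY, 2 placebo", so the nine include placebo patients. The planned numbers are 16 and 24: "A total of 24 patients may be enrolled to ensure 16 complete the study" (Protocol 10.1).
- Groups: T = 3, plus one baseline covariate.
- Post-baseline MRI visits (Protocol 2.2 and 2.3): Visits 8, 10 and 13; Visits 16 and 19 if treatment is extended; Visit 23 in follow-up. This gives V = 3 or 4 scans for a 25-week patient and 5 or 6 for a 49-week patient.
- Default rule (assumption from knowledge of the software; SAS was not run): with a RANDOM statement and no DDFM option, PROC MIXED uses containment. The patient intercept does not syntactically contain treatment, so treatment and treatment-by-visit contrasts get residual df, N − rank[X Z].

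The documents give no df, so there is no plan figure to reproduce first.

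**Visit-averaged difference**

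The 18 patient columns absorb the intercept, treatment and baseline. Visit, treatment-by-visit and baseline-by-visit add (V−1) + 2(V−1) + (V−1) = 4(V−1) columns.

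- Default df = 18V − [18 + 4(V−1)] = 14(V−1).
- Between-patient df = 18 − 3 − 1 = 14, with t(0.975) = 2.145.
- Shortfall in width = 1 − t(default)/2.145.
- Coverage = P(|t on 14 df| < t(default)).

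| Scans | Default df | t used | Too narrow by | Coverage |
|---|---|---|---|---|
| 3 | 28 | 2.048 | 4.5% | 94.0% |
| 4 | 42 | 2.018 | 5.9% | 93.7% |
| 5 | 56 | 2.003 | 6.6% | 93.5% |
| 6 | 70 | 1.994 | 7.0% | 93.4% |

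Variations:

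- Without baseline-by-visit, the default is 15(V−1), or 30 to 75.
- With 16 patients it is 24 to 60 against 12 (5.3% to 8.2% too narrow).
- With 24 patients it is 40 to 100 against 20 (3.1% to 4.9% too narrow).
- With nine patients at 4 scans and nine at 6, there are 36 + 54 = 90 scans, and 90 − (18 + 20) = 52 df against 14.

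A simulation with a true random-intercept covariance (18 patients, 40,000 runs per setting) agrees. At correlations of 0.5 to 0.95, default coverage was 93.8% to 94.1% with 3 scans and 93.3% to 93.6% with 6. At 0.2 it was 94.7% and 93.6%.

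**Single-visit difference**

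This contrast mixes between- and within-patient variance. With within-patient correlation r, the between-patient share is a = [1 + (V−1)r]/V. The Satterthwaite df is 1/[a²/14 + (1−a)²/(14(V−1))]. For V = 3 and r = 0.8, a = 2.6/3 = 0.867 and df = 1/(0.0537 + 0.0006) = 18.4. The documents give no correlation, so a range is shown.

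| r | 3 scans: df (28 used) | Limits | 6 scans: df (70 used) | Limits |
|---|---|---|---|---|
| 0.2 | 38.9 | 1.3% wide | 70.0 | nominal |
| 0.5 | 28.0 | nominal | 37.3 | 1.5% narrow |
| 0.8 | 18.4 | 2.3% narrow | 20.0 | 4.4% narrow |
| 0.95 | 15.0 | 3.9% narrow | 15.2 | 6.3% narrow |

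Setting the Satterthwaite df equal to 14(V−1) gives a = 2/V, that is, r = 1/(V−1). Single-visit limits are too narrow only above that value: 0.5 with 3 scans, 0.2 with 6.

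**The case against.** The code is illustrative and optional. It cannot run as printed, since it names `baseline` where the covariate is `baseline_volume` and misspells an ODS table name. SAP 5.6.2 names no primary MRI contrast, and no decision hangs on these limits. If the model were instead coded with a REPEATED statement and no RANDOM statement, the software's default rule would differ and this mechanism would not arise. The larger df also lean on favourable counts: 5 or 6 scans for everyone requires every patient to take the optional extension, and using Visit 23 pools week 37 for 25-week patients with week 61 for 49-week patients.

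Most of this stands, and it limits the importance. It does not remove the error. Once the names are corrected, the code gives the wrong multiplier for the visit-averaged contrast at every scan count and sample size examined, including the smallest case of 3 scans.

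A reader might go further and infer that every contrast from this code has only about 14 df, so that all its limits are too narrow. The documents do not support that. The same line requests single-visit differences, whose proper df depend on a correlation given nowhere; at low correlation the default limits are nominal or slightly wide.

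**Conclusion.** The point holds for the visit-averaged treatment differences. With 18 complete patients the default uses 28 to 70 df instead of 14. For single-visit differences it holds only if within-patient correlation exceeds 1/(V−1). The exact df depend on how many patients contribute and on scans per patient, so 28 to 70 is a range for 18 complete patients and not a fixed property of the plan. The conclusion rests on PROC MIXED's containment default and on a correct random-intercept covariance. The loss is about 1 to 1.6 points of coverage in an optional, exploratory analysis: minor, but a plain coding error.

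**What to change.** Add `ddfm=kr` (Kenward-Roger) to the MODEL statement in SAP 5.6.2 and name the method in the text; Satterthwaite would also be acceptable. Either gives about 14 df for the visit-averaged difference with 18 complete patients, and a value suited to each single-visit difference. Do not impose 14 df on every contrast: in the simulation that over-covered single-visit differences, at 95.2% to 96.5%. Correct the `baseline` and ODS names in the same edit.

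The cost is one option. Limits for the visit-averaged difference widen slightly: at 14 df the multiplier is 2.145 instead of 1.994 to 2.048. Single-visit limits may move slightly either way.

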### 5.6.3. Amyloid scans

Patients require an amyloid scan at screening (if they haven't previously had one for another purpose). This data will be listed; it will be stated if the scan is historic or de novo. If numeric SUVR data is available this data may also be summarised and potential explored by correlations to tau burden and/or disease status.

## 5.7. Exploratory Pharmacodynamic Analyses

### 5.7.1. Pharmacodynamic Parameter Estimation

The concentration of plasma tau, and the concentration of CSF biomarkers, including tau, p-tau, A $\beta$ 1-42 and neurogranin, will be determined. Since protocol approval an additional parameter will be added to the assay; neurofilament light chain in CSF, this measure will be collected and treated as per the other parameters. Plasma and CSF biomarker data will be summarised statistically and/or illustrated graphically by time and dose. The mean change in concentration of the plasma and CSF biomarkers from predose will be evaluated.

No formal statistical analyses of these exploratory CSF/plasma biomarkers are planned.

### 5.7.2. Cognition Analyses

ADAS-Cog14, NTB, MMSE, dCDT, and ADCS-MCI-ADL24 will all be summarised and may be analysed using an MMRM with preinfusion cognitive measures as a baseline covariate and fixed effects of dose and study visit. All cognition analyses are exploratory and underpowered to detect a clinically meaningful effect.

The digital clock test (dCDT) will be summarised by parameter and treatment, an MMRM may be applied.

Correlations between cognition endpoints (including dCDT) and flortaucipir F 18 SUVR, other imaging endpoints and plasma tau may be explored.

### **5.7.3. *Exploratory Pharmacokinetic/Pharmacodynamic Analyses***

A model-based approach may be implemented using NONMEM or other appropriate software to estimate PK/PD parameters. Exploratory analyses may be conducted to characterise the relationship between changes in cognition endpoints, plasma and/or CSF biomarkers and exposure of LY3303560.

### **5.7.4. *Interim Analyses***

No interim analyses are planned for this study. If an unplanned interim analysis is deemed necessary, the Lilly clinical pharmacologist, clinical research physician/investigator, or designee will consult with the appropriate medical director or designee to determine if it is necessary to amend the protocol.

The Lilly study team will review safety data obtained on an ongoing basis, to assure patient safety. Safety and/or PK interim access to data (IAD) reviews are scheduled to occur throughout the study.

Changes to any Safety reviews/IADs will not constitute a SAP amendment.

#### **5.7.4.1. *Safety reviews for dose escalation, 16 week reviews per cohort, quarterly safety reviews and end of cohort reviews***

For safety reviews it is planned that the draft site data will be loaded into Spotfire to look for trend over time and treatment. The endpoints to review will include (but not restricted to): vital signs, QTc, laboratory values, PK, and MRI scans. ADA titres will be reviewed as and when available. AEs, Conmeds and site feedback will also be reviewed (not in Spotfire)

The investigator will remain blinded and the Lilly study team will be unblinded during these reviews for dose escalation.

#### **5.7.4.2. *Internal decision making IAD for Phase 2/3 trigger***

No longer applicable.

### **5.7.5. *Other IADs***

Additional IADs may also be conducted to summarise data for internal decision making and/or supporting subsequent clinical studies/regulatory agency/IB annual updates, as required by the Lilly study team and will be articulated in the snapshot plan.

## **5.8. *Clinical Trial Registry Analyses***

Additional analyses will be performed for the purpose of fulfilling the Clinical Trial Registry (CTR) requirements.

Analyses provided for the CTR requirements include the following:

Summary of adverse events, provided as a dataset which will be converted to an XML file. Both Serious Adverse Events and ‘Other’ Adverse Events are summarised: by treatment group, by MedDRA preferred term.

- An adverse event is considered ‘Serious’ whether or not it is a treatment emergent adverse event (TEAE).
- An adverse event is considered in the ‘Other’ category if it is both a TEAE and is not serious. For each Serious AE and ‘Other’ AE, for each term and treatment group, the following are provided:
  - the number of participants at risk of an event
  - the number of participants who experienced each event term
  - the number of events experienced.
- Consistent with [www.ClinicalTrials.gov](http://www.ClinicalTrials.gov) requirements, ‘Other’ AEs that occur in fewer than 5% of patients/subjects in every treatment group may not be included if a 5% threshold is chosen (5% is the minimum threshold).
- AE reporting is consistent with other document disclosures for example, the CSR, manuscripts, and so forth. AE reporting is consistent with other document disclosures for example, the CSR, manuscripts, and so forth.

